## **7.5 Follow-up for Adverse Events**

In the case of an adverse event, participants will be referred to the neighboring UNC hospital. All follow-up visits and procedures regarding adverse events will be handled through the UNC Hospital system. A representative from our team will call the participant one week after the adverse event occurs to check-in.

## **7.6 Safety Monitoring**

The investigator will monitor subject data, without a safety monitoring board. The investigator and team will meet weekly to review safety concerns, unanticipated problems or adverse events.

## **8. INTERVENTION DISCONTINUATION**

Subjects may withdraw from the trial at any time at their own request, or they may be withdrawn at any time at the discretion of the Investigator or Sponsor for safety, behavioral or administrative reasons.

The Investigator may discontinue a subject if, in the opinion of the Investigator, the subject is no longer a suitable candidate for the study. Possible reasons for the discontinuation of a subject are including but not limited to: adverse event, protocol deviation, missed appointment, subject no longer meets the eligibility criteria.

Patients may be removed from the study due to an allergic reaction to a mouth rinse or due to failure or inability to comply with study procedures.

If a patient suffers from xerostomia/dry mouth, such that s/he cannot produce the baseline salivary sample volume or the immediate, 15 minute and 30 minute post-rinse saliva volumes, s/he will be removed from the study with a parking voucher, but without a gift card and will be replaced. If a patient suffers from dry mouth, such that s/he cannot produce salivary sample volumes needed for later time points (45 minutes or 60 minutes post-rinse) but s/he produced sufficient baseline, immediate, 15 minute and 30 minute post-rinse samples, s/he will still be compensated with a gift card and parking vouchers, and will remain in the study. Missing or deficient salivary samples will be noted in CDART.

## **9. STATISTICAL CONSIDERATIONS**

### **9.1 General Design Issues**

A double-blinded, randomized controlled trial was chosen as the study design. It allows us to collect human based data on the effects of commercially available mouthrinses on salivary infectivity and viral load. A crossover study was not pursued because the repeated use of different mouthrinses is likely to confound the results. A 1 hour time-course was chosen to correspond with the average length of most dental procedures. Fifteen minute intervals were chosen to evaluate viral kinetics over time, and to see when infectivity rebounds post- mouthrinse.

#### **Statistical Hypothesis**

The central hypotheses of this study are that a 60 second antiseptic mouth rinse will effectively reduce detectable viral RNA and protein antigen levels of SARS-CoV-2 for a minimum of 30 minutes duration.

The tertiary hypotheses are that a 60 second antiseptic mouth rinse will effectively reduce viral infectivity (>50%) of SARS-CoV-2 for a minimum of 30 minutes duration, and that mouth rinses will be well tolerated in a clinical care setting by a majority of patients and providers.

#### **Sample Size Considerations**

Based on similar viral infectivity studies evaluating antiviral mouth rinse efficacy, we were able to run power calculations to estimate effect size and determine sample size as a function of length of mouthrinse time course. The sample size is justified by a paired t-test on outcomes between time points. With three simultaneous comparisons (T1-T0, T2-T1, and T2-T0 = 30 minute time course), the sample size n=6 can detect the effect size in Cohen's  $d=0.7$ , which is between medium and large, over 80% power and 0.016 type-I error rate by Bonferroni correction. With six simultaneous comparisons (T1-T0, T2-T1, T2-T0, T3-T0, T3-T2, T3-T1) = 45 minute time course, the sample size n=53 can detect the effect size in Cohen's  $d=0.7$ , which is between medium and large, over 80% power and 0.016 type-I error rate by Bonferroni correction. With ten simultaneous comparisons (T1-T0, T2-T1, T2-T0, T3-T0, T3-T2, T3-T1, T4-T3, T4-T2, T4-T1, T4-T0) = 60 minute time course, the sample size n=78 can detect the effect size in Cohen's  $d=0.7$ , which is between medium and large, over 80% power and 0.016 type-I error rate by Bonferroni correction.

Statistical analysis of our data will be performed by [name], the statistician on this project.

#### **Primary Outcomes**

The analyses will compare viral RNA level (qRT-PCR) and protein antigen level (sandwich ELISA or rapid antigen) of SARS-CoV-2 between mouth rinse types and across the time course.

Data generated from the qRT-PCR and sandwich ELISA or rapid antigen assays will be presented as mean standard deviation for normally distributed data and as median [Interquartile range] for

non-normally distributed data. P values will be reported as two tailed. Between group comparisons will be performed using a Student's t test or Mann-Whitney U test. Normality will be assessed using the Kolmogorov-Smirnov test, and logistic regression will be performed with robust standard errors.

### **Tertiary Outcomes**

The viral infectivity analysis will compare infectivity levels between mouth rinse types and across the time course for calculation of the reduction factor (RF). The RF will be calculated as the difference in the quotient of the infection titre before ('control titration') and after the mouthrinse ('remaining virus'). Therefore, the log10 titre and its (double) standard deviation (SD) were calculated as well as the variance of the RF.

Survey- Statistical analysis will be conducted by Odum Institute's statistical consultant, [name]. We will use descriptive statistics, frequency counts and means to evaluate feasibility and acceptability of using point-of-care mouthrinses in clinical workflow.

## **9.2 Sample Size and Randomization**

Based on similar viral infectivity studies evaluating antiviral mouth rinse efficacy, we were able to run power calculations to estimate effect size and determine sample size as a function of length of mouthrinse time course. The sample size is justified by a paired t-test on outcomes between time points. With three simultaneous comparisons (T1-T0, T2-T1, and T2-T0 = 30 minute time course), the sample size n=6 can detect the effect size in Cohen's d =0.7, which is between medium and large, under 80% power and 0.016 type-I error rate by Bonferroni correction. With six simultaneous comparisons (T1-T0, T2-T1, T2-T0, T3-T0, T3-T2, T3-T1) = 45 minute time course, the sample size n=53 can detect the effect size in Cohen's d =0.7, which is between medium and large, under 80% power and 0.016 type-I error rate by Bonferroni correction. With ten simultaneous comparisons (T1-T0, T2-T1, T2-T0, T3-T0, T3-T2, T3-T1, T4-T3, T4-T2, T4-T1, T4-T0) = 60 minute time course, the sample size n=78 can detect the effect size in Cohen's d =0.7, which is between medium and large, under 80% power and 0.016 type-I error rate by Bonferroni correction.

[name], who is the statistical consultant on this project, will create a block randomization schedule and perform these computations. All patients will be consented and then fill out our screening questions for inclusion and exclusion to confirm eligibility prior to being assigned to the randomization schedule.

The researcher responsible for collecting the salivary samples will be blinded to the mouthwash solution, as they will be given a pre-aliquoted mouthrinse in an unlabeled storage syringe to provide to the patient for the rinse. The syringe will be opaque to mask any coloring of the solution.

The PI, Co-I, study coordinators and study personnel who work for GoHealth are authorized to break the blinding if a patient suffers an allergic or adverse reaction to one of the mouthrinses. Though highly unlikely as all mouthrinses are sold commercially at Walgreens and CVS, adverse or allergic reactions are possible. Using the numerical code associated with the participant and mouthrinse syringe, the study personnel can reference the block randomization schedule to determine the mouthrinse type, to inform the emergency medical workers, poison control or the emergency room what type of mouthrinse product led to the reaction.

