After the participant expectorates the mouth rinse, research staff will collect another salivary sample (T0, 2 mL over 5 minutes). During a 10 minute recuperation period, the study participants will answer demographics survey questions and questions regarding the taste, color, flavor and general acceptability of using the mouthrinse as part of routine dental and medical visits. Patients will be asked to smell an ammonia ampule (“smelling salts”) to evaluate sense of smell, as loss of olfaction is indicative of the acute infection phase. At 15 minutes post-rinse, the participant will be asked to provide an additional saliva sample (2 mL over 5 minutes), followed by another 10 minute recuperation period. This sequence will be repeated for at the 30, 45 and 60 minute time points post rinse. At 60 minutes, the study participant will give their final salivary sample (2 mL over 5 min), and study participation will conclude.

All salivary samples will be collected on ice in sterile 15 mL conical vials labelled “COVID Core” and using pre-printed labels including patient’s random alphanumeric study ID. Saliva samples will be cataloged and stored at the UNC Delta COVID Translational Initiative (also known as the Covid-19 Core) for future qRT-PCR, viral infectivity, and rapid antigen or sandwich ELISA assays. Samples will be transported on ice from the collection site to 4403A Koury Hall in leak proof biohazard bags. Samples will be processed according to the **sample processing and outcomes** procedure (below).

Following study participation completion, participants will receive \$50 compensation in the form of a Visa gift card.

During the period that the COVID+ study participants are present in the clinic and giving saliva samples, we will monitor oxygen saturation and inquire about their comfort. If participants exhibit signs of distress or if oxygen saturation drops, research study staff will contact emergency medical responders (present in the building) to visit the patient and if deemed appropriate, the participants will be escorted to UNC hospital (adjacent building).

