### **9.4 Interim Analyses and Stopping Rules**

An interim analysis will be conducted after 120 patients are enrolled and samples collected; block randomization will be planned to randomize in batches of 120 participants, with 20 randomized to each mouthrinse. Therefore, we can do an interim analysis with an  $n=120$ . This sample size is sufficient to determine antiviral efficacy at 30 minutes post-mouthrinse. If mouthrinses are ineffective at reducing viral infectivity at timepoints 15 and 30 minutes, then that mouth rinse arm will be discontinued for further enrollment and will be removed from the block randomization calendar, with initiation of a subsequent trial with fewer arms. This will allow us to enroll sufficient numbers of patients to statistically evaluate longer time point efficacy for the mouthrinses with antiviral efficacy (the longer time points require larger samples sizes for sufficient statistical power).

If no mouthrinse has antiviral effects at this interim analysis point, the study will be stopped due to lack of efficacy. Because all oral rinse products are commercially available, low risk products that have previously undergone extensive safety testing and approval procedures, we do not anticipate a situation where safety concerns to participants necessitates halting the study. Adverse events will be reported and reviewed by our internal quality control committee. Medical problems that occur in our facility will be reported as needed to the IRB board and emergency medical personnel will be contacted to care for the patient and potentially bring them to the adjacent UNC medical hospital. If a significant number of adverse events or reactions are witnessed (defined as more than 1 per every 20 patients), a safety review will be triggered and study personnel will look at the records in an unblinded fashion to see if one mouthrinse is causing reactions. If that is the case, the mouthrinse study arm associated with adverse events will

be discontinued, but the mouthrinse arms associated with minimal adverse events will continue.

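### The stated n=6 gives about 13% power, not 80%, at d=0.7 on the SD of differences; 0.016 fits only three comparisons, and 6, 53 and 78 do not come from one calculation

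*Combined protocol and SAP*

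**What the plan says.** Section 9.2 names the test: "The sample size is justified by a paired t-test on outcomes between time points". It then gives three sample sizes, all at d=0.7.

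- Three comparisons: "With three simultaneous comparisons (T1-T0, T2-T1, and T2-T0 = 30 minute time course), the sample size n=6 can detect the effect size".
- Six comparisons: "With six simultaneous comparisons (T1-T0, T2-T1, T2-T0, T3-T0, T3-T2, T3-T1) = 45 minute time course, the sample size n=53 can detect" the same effect.
- Ten comparisons (60-minute course): n=78.

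Each figure carries the same qualifier: "which is between medium and large, under 80% power and 0.016 type-I error rate by Bonferroni correction". Sample Size Considerations in section 9.1 repeats the three figures with a slightly different phrase: "which is between medium and large, over 80% power and 0.016 type-I error rate by Bonferroni correction". Sections 2.2 and 9.6 repeat the ten-comparison figure with the same 0.016. Section 9.1 (Primary Outcomes) and section 9.6 say that P values are two-tailed. The planned enrolment is 80 per rinse.

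Section 9.4 plans an interim look at 120 patients, 20 per rinse, and says: "This sample size is sufficient to determine antiviral efficacy at 30 minutes post-mouthrinse". It adds that "the longer time points require larger samples sizes for sufficient statistical power". An arm judged ineffective at 15 and 30 minutes is closed to enrolment, and the study stops if no rinse works.

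**The concern.** Six pairs is very few to detect a standardised difference of 0.7 at a level below 0.02. A Bonferroni level must also fall as the number of comparisons rises, but here it stays at 0.016 for three, six and ten. If the level really were constant, the required n would not change with the number of comparisons at all, so a rise from 6 to 53 to 78 needs some other explanation.

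No arm or look uses n=6, so the first issue is that the stated figures are wrong and cannot be reproduced. The second is the interim look, which can close arms. Section 9.4 takes 20 per arm as enough at 30 minutes and says later time points need more. The only 30-minute sample size in the plan is the n=6 figure.

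**Working it through.** **Inputs.** From sections 9.1 and 9.2: paired t-test, d=0.7, 80% power, level 0.016, two-sided, with n = 6, 53 and 78 for 3, 6 and 10 comparisons. From section 9.4: 20 per arm at the interim. From the Précis: 80 per arm. Assumed, because the plan does not state them: familywise alpha 0.05, the SD that scales d, and the within-person correlation ρ.

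**Formula.** Power = P(|T| > t(1−α/2, n−1)), where T is noncentral t with n−1 degrees of freedom and noncentrality dz·√n.

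- d on the SD of the differences: dz = 0.7.
- d on the raw SD: dz = 0.7/√(2(1−ρ)), which is 0.495 at ρ=0 and 0.990 at ρ=0.75.

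**Step 1: the stated n=6.** With dz=0.7 the noncentrality is 0.7×√6 = 1.715 and the critical value at two-sided 0.016 is 3.573. Power is 12.7%. At 24 pairs it is 78.9% and at 25 it is 81.0%, so 25 are needed. Other readings of n=6:

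| Reading | Power at n=6 |
|---|---|
| One-sided 0.016 | 21% |
| Two-sided 0.05, unadjusted | 29% |
| One-sided 0.05, unadjusted | 43% |
| Raw SD, two-sided 0.016, ρ = 0 / 0.25 / 0.5 / 0.75 | 7% / 9% / 13% / 26% |

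Reaching 80% with six pairs needs dz of about 1.88 at 0.0167, which on the raw SD means ρ of about 0.93.

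**Step 2: the level.** 0.05/3 = 0.0167, 0.05/6 = 0.0083 and 0.05/10 = 0.005. Using 0.016 throughout gives Bonferroni bounds of 3×0.016 = 0.048, 6×0.016 = 0.096 and 10×0.016 = 0.160. Whatever the familywise level, one value cannot be the Bonferroni level for all three counts.

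**Step 3: one calculation for all three n.** For 80% power, two-sided:

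| | 3 comparisons (0.0167) | 6 (0.0083) | 10 (0.005) |
|---|---|---|---|
| Stated | 6 | 53 | 78 |
| d on SD of differences | 25 | 29 | 32 |
| d on raw SD, ρ=0 | 46 | 53 | 59 |
| ρ at which the stated n gives 80% (raw SD) | 0.93 | 0.00 | −0.36 |

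Only 53 reproduces. Taking 0.016 literally for all three gives 25 throughout (SD of differences) or 47 throughout (raw SD, ρ=0).

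**Step 4: the planned 80 per arm.** At two-sided 0.005, power is 99.95% with dz=0.7 and 93.4% with d on the raw SD at ρ=0. It is higher for any positive ρ.

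**Step 5: 20 per arm.** Section 9.4 gives no contrast, alpha or effect size. If d=0.7 and two-sided 0.0167 are assumed for a within-arm contrast, power is 69% on the SD of differences. On the raw SD it is 36% at ρ=0, about 80% at ρ=0.6 and 95% at ρ=0.75.

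**Step 6: which samples are compared.** Section 3 labels as T0 the sample taken after the rinse: "After the participant expectorates the mouth rinse, research staff will collect another salivary sample". The ten listed contrasts are the ten pairs among the five post-rinse samples. None of them is a fall from the pre-rinse sample.

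**The case against.** **A lost digit.** The reading that reproduces 53 gives 46 for three comparisons, so the 6 may be 46 with a digit dropped and copied between two near-identical sections. This is plausible, but the documents cannot confirm it, and 78 would still not fit (59). It also means that 25 should not be read as the correct n. It follows only if d is on the SD of the differences, which the plan does not say.

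**The interim.** A reader might infer that 20 per arm is underpowered and that effective rinses will be dropped. The documents do not support that.

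- Section 9.4 does not cite n=6 or d=0.7.
- Within-person correlations above about 0.6 would put power at 20 above 80% on the raw-SD reading.
- The interim concerns infectivity, for which sections 1.2 and 9.5.2 hypothesise a fall of more than 95%, or −log10(0.05) = 1.30 log10. For assumed SDs of the paired difference of 1.0, 1.5 and 2.0 log10, n=20 at 0.0167 has over 99%, 88% and 62% power. The >50% target under Statistical Hypothesis in section 9.1 would give far less.
- If an arm must fail at both 15 and 30 minutes, and failure means non-significance (both assumed), the chance of wrongly dropping it is below the 31% miss rate of a single contrast at dz=0.7. In simulation it was 10% to 21% for correlations between the two contrasts of 0 to 0.8.

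This objection stands. The interim statement is unsupported, not refuted.

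**The trial as a whole.** A reader might also infer that the final sample is too small. Step 4 shows otherwise for the paired test.

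**Wording of the power.** The difference between sections 9.1 and 9.2 in the word before 80% power may only mean that these are the conditions of the calculation. Nothing here rests on it.

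**Conclusion.** The stated 30-minute sample size is wrong as written. Six pairs give 12.7% power against the stated 80%, and 7% to 43% across the variants tried. Only an unstated within-person correlation of about 0.93, or an effect far larger than 0.7 on the SD of the differences, would rescue it. The 0.016 fits three comparisons only, given an assumed familywise 0.05. The three sample sizes cannot share one calculation.

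The consequence is limited. The planned 80 per arm has at least 93% power for the paired test at 0.005, with d on the SD of the differences or on the raw SD with zero or positive correlation. The adequacy of 20 per arm at 30 minutes remains undemonstrated: the plan lacks the inputs either to confirm or to reject it. This should be corrected, but it does not undermine the final sample size for the paired test.

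**What to change.** 1. Settle which contrasts are tested, including those from the pre-rinse sample. This comes first because it sets the Bonferroni divisor. For the 30-, 45- and 60-minute courses, all pairs including the pre-rinse sample number 6, 10 and 15. Pre-rinse against each post-rinse sample gives 3, 4 and 5.
2. In sections 2.2, 9.1, 9.2 and 9.6, state the SD that d=0.7 refers to, any assumed within-person correlation, and the familywise alpha.
3. Restate each n, or the power that the chosen n delivers, at the Bonferroni level for that number of contrasts. This replaces n=6 and the blanket 0.016.
4. In section 9.4, replace the sufficiency sentence with the power at 20 per arm for a named contrast, alpha and effect size.

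The cost is protocol wording and a short recalculation, with no extra patients. The downside is that the stated interim power may look less favourable than the present text implies.

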## Summary of Inclusion and Exclusion Criteria for Mouthrinse RCT

Inclusion Criteria	Exclusion Criteria

Individuals (all sex, all gender) at least 18 years of age and at most 65 years of age in good oral health and with stable physical health, decided at the discretion of the study coordinator.
	
Known allergies or significant adverse reactions following the use of oral hygiene products (toothpastes, mouthrinses), commercial cosmetics, iodine, and any ingredient in the mouthrinses (list will be provided).

Diagnosed COVID+ status (within the past 48 hours) who became symptomatic in the prior 10 days, or if not symptomatic, was likely infected/exposed within the prior 10 days.
	
Established history of Xerostomia (drug-induced or autoimmune dry mouth), renal disease, thyroid problems (including swelling, Hoshimoto's thyroiditis, Goiter), Hepatitis C Virus (HCV), severe periodontal disease with bleeding gums, significant oral abrasions/ulcers or growths, alcohol abuse, recreational drug abuse, and/or current treatment with lithium. Other severe acute or chronic medical or psychiatric condition or laboratory abnormality that may increase the risk associated with trial participation or investigational product administration or may interfere with the interpretation of trial results and, in the judgment of the Investigator, would make the subject inappropriate for entry into this trial.

Evidence of a personally signed and dated informed consent document indicating the subject (or legally acceptable representative) has been informed of all pertinent aspects of the trial and all of their questions have been answered.
	
Drinking or eating within an hour of the study visit. Consuming alcohol within 12 hours of the study visit. Rinsing with a commercial mouthrinse within 24 hours of the study visit.

Able to comprehend and follow the requirements of the study (including availability on scheduled visit dates) based on research site personnel's assessment.
	
Developmental/cognitive disability such that patient cannot self-consent, comprehend and follow the requirements of the study based on research site personnel's assessment.

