### 4.3 Study Enrollment Procedures

Outpatient subjects will be recruited from patients seen in the UNC Respiratory Distress Clinic (RDC) and other UNC testing facilities who have tested positive for COVID+ and consented to be contacted for participation in COVID-related research studies. The subjects are being approached by phone or email have signed a prior facility consent at the Respiratory Distress Clinic confirming their willingness to share their name and contact information to be contacted for study participation in COVID related research. We will not receive information on subjects that decline this internal consent. Subjects will be contacted for recruitment by phone and (if unreachable by phone) by secure email by study personnel; patients will have the study rationale and risks explained and will be provided time to ask questions and consider participation. If patients are interested in participating, a single appointment will be scheduled for them at the Adams School of Dentistry Go Health Clinical research core. Consent documentation will be signed in person and in private in the Go Health Clinical Research Core. For Spanish speaking patients and/or parents, Spanish forms will be provided and communication will occur through a Spanish translator. All patients are adults and over normal cognitive capacity, and therefore will be able to consent for themselves. A list of COVID+ subjects that have consented to be contacted for research, will be provided by the RDC clinic, sent via secure UNC servers or secure UNC email to our research team's clinical coordinator, and this list will include names and contact details (PHI). This list is updated daily and provided to approved research sites, including ours.

At the visit, a consented patient will answer screening questions regarding inclusion and exclusion criteria. Answers will be entered into the CDART research database managed by UNC. Prior to finalizing these screening questions, women participants of childbearing potential will be asked to provide a urine sample in the restroom, to undergo a rapid pregnancy test by study personnel. Any pregnant or lactating patients will be excluded.

Our study statistician, [name], will create a block randomization schedule and perform these computations. All patients will be consented and then fill out our screening questions for inclusion and exclusion to confirm eligibility prior to being assigned to the randomization schedule.

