### **6.2.3 Blinding**

At their onsite visit, subjects will be provided with an unlabeled/blinded mouthrinse. The researcher in charge of collecting the salivary samples will be blinded to the mouthwash solution as well, as they will be given a pre-aliquoted mouthrinse in an unlabeled storage syringe to provide to the patient for the rinse. Our statistical consultant, [name],

will set up a block randomization schedule that the team will abide by for assignment of enrolled subjects.

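### Emergency unblinding means looking up the randomization schedule itself, so one code-break could show enrolling staff upcoming assignments, and no allocation concealment is described

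*Combined protocol and SAP*

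**What the plan says.** Section 9.2 names who may unblind: "The PI, Co-I, study coordinators and study personnel who work for GoHealth are authorized to break the blinding". It states the condition, "if a patient suffers an allergic or adverse reaction to one of the mouthrinses", and the method: starting from the numerical code that links participant and syringe, "the study personnel can reference the block randomization schedule to determine the mouthrinse type". The stated purpose is to tell emergency staff or poison control which product was used.

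Section 6.2.3 says that the statistical consultant "will set up a block randomization schedule that the team will abide by for assignment of enrolled subjects". Section 9.4 plans randomization in batches of 120, with 20 per rinse.

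On entry to the trial, section 4.3 has the daily list of candidates "sent via secure UNC servers or secure UNC email to our research team's clinical coordinator". The summary table of criteria in section 4 requires participants to be "in good oral health and with stable physical health, decided at the discretion of the study coordinator". Sections 4.3, 6.2.2 and 9.2 have patients screened "to confirm eligibility prior to being assigned to the randomization schedule".

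On staying in the trial, sections 6.2.5 and 8 allow withdrawal at the investigator's discretion. Those two sections and 10.3.3 have participants who give too little saliva up to 30 minutes removed and replaced.

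The safeguards described are an unlabelled opaque syringe and a blinded saliva collector (sections 5.2, 6.2.2, 6.2.3 and 9.2).

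**The concern.** Blinding and allocation concealment protect against different things. The opaque syringe hides the current participant's rinse from the person collecting saliva. It does not hide the next participant's rinse from someone who has seen the list.

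The plan uses one document both to assign participants and to unblind them, and it gives the look-up to roles that also book and screen. After one proper code-break, a coordinator could know what the next several participants will receive. That knowledge could influence, even without intent, who is booked when, a borderline judgement of stable health, or a decision to withdraw someone. At stake is the comparability of the six arms, on which every between-rinse comparison depends.

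**Working it through.** **1. The plan's own figures.** Section 9.4: 6 rinses × 20 = 120 per batch. Four batches: 4 × 120 = 480 = 6 × 80, the total in the Précis and the section 3 table. These agree.

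**2. The passages side by side.**

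- Who may look: PI, Co-I, coordinators, GoHealth personnel (9.2).
- When: after an allergic or adverse reaction (9.2).
- What they look at: the block schedule, with no restricted view stated (9.2).
- Who works from it: the team, to assign participants (6.2.3).
- Who fills the syringes: research staff, with no stated separation from enrolment (5.2).
- Who affects entry: the clinical coordinator receives the list (4.3), and the study coordinator judges stable health (section 4 summary table).
- Who affects retention: the investigator (6.2.5, 8) and, for short saliva, the staff collecting samples (10.3.3).
- Central assignment, sealed envelopes, one-record reveal, independent custodian, access log: none found.

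**3. Predictability of the next assignment.**

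- Concealed: 1/6 = 16.7%.
- Only past assignments known, each batch treated as one permuted block of 120, best guess from the remaining counts: about 24% (simulation of 4,000 blocks).
- Schedule seen: 100%.

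If a batch is a single block, its size protects well against guessing. It gives no protection against reading the list.

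**4. How much one look could show.** A look-up after participant k of a batch leaves 120 − k assignments ahead: 119 after the first, 60 after the sixtieth, none after the last. This assumes that the list covers the current batch. The plan does not say whether it covers more or less.

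**5. How often an occasion might arise.** P(at least one) = 1 − (1 − p)^n. Section 2.2 puts allergy below 1%. No rate is given for other adverse reactions, which also permit unblinding, so p is an assumption.

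| Assumed reaction rate p | n = 120 | n = 480 |
|---|---|---|
| 0.1% | 1 − 0.999^120 = 11% | 1 − 0.999^480 = 38% |
| 0.5% | 1 − 0.995^120 = 45% | 1 − 0.995^480 = 91% |
| 1% | 1 − 0.99^120 = 70% | 1 − 0.99^480 = 99% |

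These are chances that a look-up is called for, if every reaction leads to one. They are not chances that anyone misuses what they see.

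**The case against.** The strongest reply is that access is narrow. It is authorised only after a reaction, starts from one participant's code, and serves an emergency that section 9.2 itself calls highly unlikely. The layout and custody of the schedule are not given, so a look might show one line or one batch. Having the team follow a schedule does not mean that enrolling staff see it; coded syringes filled by others would fit the same words. All of this stands, and it rules out a reading that a reader might infer: that staff have standing access to the full list and that assignments are in fact unconcealed.

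Steering would also be hard. Viral load is not measured at enrolment; section 6.2.4 runs no diagnostic tests, and section 9.5 places the assays weeks to months later. Staff would have only crude proxies. Coordinator discretion appears only in the summary table, most criteria are enumerated, and the saliva rule rests on volume markings. This limits the likely bias without removing the route.

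A reader might also want to attach a false-positive rate. An imbalance of 0.1, 0.2 or 0.3 SD with no rinse effect, at 80 per arm and an unadjusted two-sided 5% t test, gives 10%, 24% or 47%. The arithmetic is right, but the shifts have no source in the documents. The figures also assume steering averaged over all 80 participants in an arm, whereas a reaction-triggered look affects only later ones. And they ignore the ANCOVA in section 9.6. If the same shift affects baseline and post-rinse values, ANCOVA multiplies the noncentrality δ√(n/2) by √((1 − ρ)/(1 + ρ)). At assumed correlations ρ of 0.5, 0.7 and 0.9, the 47% falls to 19%, 12% and 7%. No such rate belongs in the conclusion.

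Two parts of the reply fail. Confirming eligibility before assignment fixes the order of steps but does not hide the next line from someone who has seen it. ANCOVA does not cover everything either: section 9.6 also lists unadjusted between-group tests, and baseline adjustment cannot undo selective removal after the rinse.

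**Conclusion.** The point holds as a weakness in a stated procedure. The plan unblinds through the schedule used for assignment, restricts the view nowhere and describes no concealment. That one look could expose upcoming assignments is an inference from the unrestricted wording. The documents do not show that concealment has been or will be breached.

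For a person who has seen the list, the chance of knowing the next assignment goes from 16.7% to 100%, for up to 119 participants if the list covers one batch. Whether an occasion arises depends on the assumed reaction rate: 38% to 99% over 480 participants at 0.1% to 1%. The effect on the results cannot be quantified from the documents and is probably modest, for the reasons given above. The change should be made because it is cheap and the trial is presented as randomized and double-blinded. No sample-size figure is affected.

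**What to change.** In sections 9.2 and 6.2.3:

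- Replace the schedule look-up with a single-participant code-break: a numbered sealed envelope or a one-record reveal in CDART, available immediately in an emergency, with each use logged.
- Limit the schedule to the statistician and the existing staff member who fills the coded syringes. That person takes no part in screening, enrolment, saliva collection or withdrawal decisions. The preparer has to be named because section 5.2 leaves preparation to research staff, so the statistician cannot be the only holder.
- Release each assignment only after eligibility has been recorded.

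The cost is protocol wording, a set of envelopes or one CDART field, and a division of tasks among existing staff. Emergency access is kept.
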